8.11.1. Management of treatment dose adaptations due to trifluridine/tipiracil toxicities

All toxicities related to trifluridine/tipiracil must have resolved to Grade 1 or baseline before the start of a new treatment cycle.

In the event of haematological and/or non-haematological toxicities, rules for trifluridine/tipiracil dose interruption and resumption are provided in [Table \(8.11.1\) 1](#); rules for dose modifications are provided in [Table \(8.11.1\) 2](#) and [Table \(8.11.1\) 3](#).

Treatment interruptions are regarded as lost treatment days and missed doses should not be replaced; the planned treatment schedule should be maintained.

A new treatment cycle with trifluridine/tipiracil can be started only if neutrophils count is $\geq 1.5 \times 10^9/L$ and platelets count is $\geq 75 \times 10^9/L$.

Table (8.11.1) 1 - Dose interruption and resumption criteria for haematological toxicities related to myelosuppression

Parameter	Interruption criteria*	Resumption criteria**
Neutrophils	$< 0.5 \times 10^9/L$	$\geq 1.5 \times 10^9/L$
Platelets	$< 50 \times 10^9/L$	$\geq 75 \times 10^9/L$

* Interruption criteria apply only during active treatment intake period (i.e., D1-5 and D8-12) based on an unscheduled laboratory assessment.

**Resumption criteria apply to the start of the next cycle for all participants regardless of whether or not the interruption criteria were met.

Table (8.11.1) 2 - Recommended dose modifications in case of haematological adverse event related to myelosuppression

Adverse event related to myelosuppression	Recommended dose modifications
Febrile neutropenia NCI-CTCAE Grade 4 neutropenia count $< 0.5 \times 10^9/L$ that results in more than 1 week's delay in start of next cycle	Don't start a new treatment cycle until the resumption criteria are met (Table (8.11.1) 1) When resuming dosing, decrease the dose level by 5 mg/m ² from the previous dose level (Table (6.1.3.2) 2)
NCI-CTCAE Grade 4 thrombocytopenia $< 25 \times 10^9/L$ that results in more than 1 week's delay in start of next cycle	Dose reductions are permitted to a minimum dose of 20 mg/m ² /dose twice daily Do not increase dose after it has been reduced

Table (8.11.1) 3 - Recommended dose modifications in case of non-haematological adverse event related to trifluridine/tipiracil

Adverse event related to trifluridine/tipiracil	Recommended dose modifications
NCI-CTCAE non-haematologic grade 3 or 4 adverse reaction; except for grade 3 nausea and/or vomiting controlled by antiemetic therapy or diarrhoea responsive to antidiarrheal medicinal products.	Don't start a new treatment cycle until toxicity resolves to Grade 1 or baseline When resuming dosing, decrease the dose level by 5 mg/m ² from the previous dose level (Table (6.1.3.2) 2) Dose reductions are permitted to a minimum dose of 20 mg/m ² /dose twice daily Do not increase dose after it has been reduced

If the participant recovers from toxicities requiring treatment interruption:

- During the 2-week active treatment intake period of a cycle (treatment D1-D12):
 - If no dose reduction is required, trifluridine/tipiracil may be resumed during that cycle. Missed doses must not be caught up.
 - If a dose reduction is required, trifluridine/tipiracil should be resumed at the start of the next treatment cycle at the appropriate dose level.
- During the rest period (D13-28):
 - Start the next cycle on schedule at the appropriate trifluridine/tipiracil dose level.

If the toxicity does not resolve during the given cycle to Grade 1 or baseline, the start of the next cycle may be delayed by a maximum of 30 days from the last dose of trifluridine/tipiracil administered to allow the initiation of both IMPs at the same time in the next cycle. If more than 30 days from the last dose administered are needed for recovery, the next cycle should be started by omitting trifluridine/tipiracil doses as needed (i.e. next cycle is started with only S95026 and trifluridine/tipiracil is reintroduced later) or the participant may have trifluridine/tipiracil discontinued, according to investigator's judgement.

Note: Interruption/resumption criteria and recommended dose modifications of trifluridine/tipiracil could be done in accordance with the local SmPC (Summary of Product Characteristics)).

8.11.2. Management of treatment dose adaptations due to futuximab/modotuximab toxicities

Anticipated AEs that may be experienced with futuximab/modotuximab are detailed in this protocol ([Section 2.6](#) and [Section 2.8](#)), as well as in the Investigator's Brochure (IB). Participants will be evaluated throughout the course of the trial for acute as well as delayed and/or cumulative toxicities.

If a significant toxicity thought to be related to futuximab/modotuximab is experienced at any point during the participant's participation in the study, the investigator will determine appropriate management, including determining whether that toxicity warrants a change in premedication ([Section 6.1.2](#)), or a dose modification such as infusion prolongation (in the event of an IRR) ([Section 8.11.2.1](#)), temporary dose delay ([Section 8.11.2.2](#)), or dose reduction ([Section 8.11.2.3](#)).

8.11.2.1. Decrease of infusion rate

For IRRs, infusion prolongation instructions are provided in [Section 8.12.4.1](#).

To enhance participant safety following an infusion prolongation, subsequent infusions will be administered with a lower infusion rate at the prolonged rate.

8.11.2.2. Dose Delay

Toxicities may be managed by delay in dosing, provided they do not meet the criteria for IMP discontinuation ([Section 5.8.1](#)). In such cases, the period between any 2 scheduled doses may be extended up to 3 days (inclusive) to allow an improvement of the toxicity. Such delays will be considered an extension within the current cycle. If a delay of more than 3 days from the scheduled dose date is necessary, the dose should be omitted and proceed to the next scheduled dose (i.e. 14 days from the last dose).

If 3 consecutive doses are needed to be omitted (i.e. more than 21 days from the last dose of futuximab/modotuximab), the participant should be discontinued from futuximab/modotuximab. All delays of futuximab/modotuximab must be documented on the appropriate page of the participant's e-CRF.

If toxicity does not resolve during the given cycle to Grade 1 or baseline, the start of the next cycle may be delayed by a maximum of 21 days from the last dose of futuximab/modotuximab administered to allow the initiation of both IMPs at the same time in the next cycle. If more than 21 days from the last dose administered are needed for recovery, futuximab/modotuximab should be discontinued and the next cycle will start with only trifluridine/tipiracil.

Dosing may be restarted at the same dose, as clinically indicated. However, administration of futuximab/modotuximab may only be restarted provided retreatment criteria are met ([Section 6.1.5](#)).

For treatment restart with no dose reduction:

- If treatment restart after the omission of 1 dose (i.e. treatment delay up to 14 days from the last dose), it is recommended that dosing restart with maintenance dose of 6 mg/kg;
- If treatment restart after the omission of 2 consecutive doses (i.e. treatment delay up to 21 days from the last dose), it is recommended that dosing re-start with the re-administration of a loading dose of 9 mg/kg followed by weekly maintenance doses of 6 mg/kg.

For treatment restart with dose reduction, see Section 8.11.2.3.

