6.1.1. Administration of futuximab/modotuximab

6.1.1.1. Dose

- Loading dose: 9 mg/kg on C1D1.
- Maintenance doses: 6 mg/kg weekly (\pm 2 days), beginning on C1D8.

The dose level of futuximab/modotuximab to be administered will be multiplied by the participant's weight in kilograms to arrive at the total dose to be delivered. During the Randomised part the number of vials needed for each dose will be automatically calculated by the IWRS based on weight as measured at the beginning of each cycle. Participants will continue to be treated with futuximab/modotuximab at that same assigned dose throughout the duration of the treatment period unless dose reduction is required.

Dose adjustments should be made in the event of noted weight change (\pm 10%) as measured at the beginning of dosing cycle (CxD1). Weight fluctuations due to "third-space"/interstitial fluid accumulation (e.g., oedema, ascites, pleural effusion) or medications that result in fluid retention (e.g., glucocorticoids) do not require dose adjustment.

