6.1.1.3. Schedule

- Once weekly on Day 1, Day 8, Day 15, and Day 22 (\pm 2 days) of each cycle (4 weeks [28 days] equals 1 dosing cycle).

A weekly dosing schedule is to be maintained, unless delay is required to allow for amelioration of toxicities (or in the event of scheduling difficulties associated with extended weekends, holidays, etc.). Futuximab/modotuximab should be administered after trifluridine/tipiracil intake.

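### Section 8.11.2.2 gives two incompatible triggers for permanently stopping futuximab/modotuximab: on days 22 to 24 after the last dose, the omission count allows a restart and the day limit requires a stop

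*Protocol*

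**What the plan says.** Futuximab/modotuximab is infused "Once weekly on Day 1, Day 8, Day 15, and Day 22" of each 28-day cycle, with a window of plus or minus 2 days (Protocol Sections 6.1.1.1 and 6.1.1.3).

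Section 8.11.2.2 covers delays made to manage toxicity:

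- Extension without omission: "the period between any 2 scheduled doses may be extended up to 3 days (inclusive) to allow an improvement of the toxicity".
- Definition of an omitted dose: "If a delay of more than 3 days from the scheduled dose date is necessary, the dose should be omitted and proceed to the next" planned infusion.
- Permanent stop, by count and days together: "If 3 consecutive doses are needed to be omitted (i.e. more than 21 days from the last dose of futuximab/modotuximab", futuximab/modotuximab should be discontinued.
- Permanent stop, by days alone, at the start of the next cycle: "If more than 21 days from the last dose administered are needed for recovery, futuximab/modotuximab should be discontinued".
- Restart without dose reduction: "If treatment restart after the omission of 1 dose (i.e. treatment delay up to 14 days from the last dose", 6 mg/kg is recommended; "If treatment restart after the omission of 2 consecutive doses (i.e. treatment delay up to 21 days from the last dose", a 9 mg/kg reload is recommended.

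Section 8.11 repeats a 21-day maximum delay for this drug at the start of a cycle. It refers to Sections 8.11.1 and 8.11.2 without itself saying from which date the 21 days run. Section 8.11.2.2 does not say whether the count or the days governs when they differ.

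**The concern.** Each rule joins a count to a number of days as though one restated the other. That is true only when both the last infusion and the restart infusion fall exactly on their nominal days. The same section lets a dose be given up to 3 days late without being omitted, so the two measures separate in the situation the section is written for: a participant whose toxicity is slow to resolve.

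What is at stake is mainly the stopping rule. Two sites facing the same participant on day 23 could both claim to follow the protocol, one restarting the drug and the other ending it permanently. Exposure, discontinuations and protocol deviations would then depend partly on which sentence a site reads. A smaller issue is attached to the restart dose. Section 8.5 counts any non-loading administration above 6 mg/kg as an overdose, and Section 8.7 requires overdoses to be notified within 24 hours. It should therefore be beyond doubt when a 9 mg/kg reload is within protocol.

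**Working it through.** Inputs, all from the Protocol: dosing interval 7 days and window ±2 days (6.1.1.1, 6.1.1.3); extension up to 3 days, omission only beyond 3 days, and day limits of 14, 21 and more than 21 (8.11.2.2).

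Let the last infusion be given *l* days off its scheduled date and the restart infusion *r* days off its own. After *k* omitted weekly doses, the interval since the last dose is

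D = 7(k + 1) + r − l.

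**1. The section's own figures (r = l = 0).** k = 1 gives 14 days and k = 2 gives 21 days, as stated. k = 3 gives 28 days, which is a stop by either measure. On nominal days the two measures agree.

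**2. When the third omission occurs.** With the last dose on day 0, the third dose is due on day 7 × 3 = 21. It becomes omitted only when more than 3 days late, that is after day 21 + 3 = 24. The day limit is passed from day 22. On days 22, 23 and 24 only two doses have been omitted, but more than 21 days have elapsed.

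**3. Without the extension.** If the 3-day extension is held not to apply to a restart infusion, the ±2 day window still allows an infusion up to day 21 + 2 = 23. The disputed days are then 22 and 23.

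**4. Last infusion given 2 days early (l = −2).** The third scheduled date is then 23 days after the last dose. The disputed band reaches 21 + 2 + 2 = 25 days with the window alone, or 21 + 3 + 2 = 26 days with the extension.

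**5. Restart after one omission.** The latest infusion is on day 14 + 3 = 17 with the extension, or 14 + 2 = 16 with the window. Days 15 to 17 (or 15 to 16) are one omission by count but outside the 14-day gloss. They fall within the span that the next bullet ties to two omissions. The two recommended doses differ by a factor of 9/6 = 1.5.

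| Omitted doses | Nominal day | Disputed days, extension used | Disputed days, window only | By count | By days |
|---|---|---|---|---|---|
| 1 | 14 | 15–17 | 15–16 | 6 mg/kg recommended | outside the 14-day gloss |
| 2 | 21 | 22–24 | 22–23 | restart allowed | discontinue |

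The table takes the last dose as on time.

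**6. Cases with no conflict.** Let *l* run from −2 to +2 and *r* from −2 to +3. With no omission, D runs from 3 to 12 days, never above 14. With three omissions, D runs from 24 to 33 days, always above 21.

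**The case against.** The strongest reply is that the counts are the operative conditions and the days are loose shorthand. For the restart doses this largely succeeds. Each bullet is conditioned on the number of omitted doses, both doses are recommendations for restart without dose reduction, and the summary of changes for version 3.0 also describes the reload by count. A reader might infer that the protocol prescribes both 6 and 9 mg/kg for the same infusion. It does not: no sentence recommends 9 mg/kg after a single omission. What remains is a gloss that does not match its condition.

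For the permanent stop the reply fails, because the 21-day limit also stands alone as an instruction in Section 8.11.2.2, and Section 8.11 repeats a 21-day maximum. It cannot be set aside as illustration.

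A second reply is that the stop rules are worded by need: doses that need to be omitted, or days needed for recovery. A participant who has recovered by day 21 but is infused on day 22 or 23 for scheduling reasons has arguably met neither. This has force. A reader might infer that routine visit slippage alone forces permanent discontinuation. The section concerns toxicity, and the clear conflict is toxicity still unresolved on day 21 that resolves by day 24.

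A third reply is that the section sends a participant with an omitted dose to the next scheduled date, glossed as 14 days from the last dose, so the extension may not apply to a restart. That is a possible reading. It narrows the band to the ±2 day window and does not remove it.

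**Conclusion.** The stopping rule contradicts itself as written. With the last dose on time, the disputed band is days 22 to 24 after two omissions, or days 22 to 23 if only the visit window is used. It extends to day 26 at most if the last dose was 2 days early and the extension is used. The arithmetic assumes only the intervals printed in the Protocol, plus the reading that the extension between any two scheduled doses includes a restart dose. The mismatch in the restart-dose glosses is real but secondary.

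Three wider inferences are not supported:

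- **Frequency.** The documents give neither how often doses are omitted nor how infusions spread within their windows, so no share of affected restarts can be stated. Nor does every late restart fall on the disputed side: with the last dose at +2 and the restart at +1 after one omission, D = 14 + 1 − 2 = 13 days.
- **Comparison between arms.** SAP Section 1 records that the randomised part was cancelled during the Safety Lead-In. The reach is that single-arm part, planned for about 25 participants, and within it those who restart late after omissions.
- **DLT evaluability.** Section 4.1.3.2 replaces participants who stop permanently in Cycle 1 for reasons other than a DLT, so the two readings might seem to decide who is counted. But with two Cycle 1 doses omitted, at most 9 + 9 = 18 of the planned 9 + 3 × 6 = 27 mg/kg is given. That is 67%, already below the 75% dose-intensity threshold, so evaluability turns on other rules as well.

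This is an inconsistency in wording that should be corrected. It does not show that either limit is clinically wrong.

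**What to change.** Reconcile the statements in Section 8.11.2.2 that use the number of omitted doses with those that use days since the last dose. Make both consistent with the 3-day extension, the ±2 day window in Sections 6.1.1.1 and 6.1.1.3, and the 21-day maximum in Section 8.11, so that each situation leads to one instruction. Say explicitly whether the extension and the window apply to a restart infusion. Appendix 10, Section B should be read against the result, because its note permits longer delays for dermatologic events after 2 weeks without stating an upper limit. Which measure governs, and what the limits are, is for the sponsor to decide.

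The cost is a few sentences in a protocol amendment, with no change to data collection or analysis.

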				
 - Criterion #32b was revised to add “per the investigator’s discretion” for consistency. - Text was revised in Section 6.1 regarding COVID-19, as with the advanced knowledge on the COVID-19 infection, the period to re-start study treatment can be reduced, to increase at the same time the chances to respond to treatment. - Text revised regarding size of in-filter in Section 6.1.1.2. - Text was corrected to remove “at C1D1 only” in Section 6.1.1.6. - Text in Section 6.1.5 was revised for clarity, following modifications regarding dose delays in Section 8. - Text in Section 6.3.1.1 was revised to align with wording of criterion# 40a. - Text in Section 8.2.6 was revised to align with wording of criterion# 32a. - Text regarding “Any events of COVID-19” was removed in Section 8.7 since there is no longer a reason to consider COVID-19 events as ERINs because only serious adverse events should be integrated in the PV database. - Text was revised in Sections 8.11, 8.11.1, and 8.11.2, to provide more information about dose delay and specify maximum delay periods to allow initiation of both IMPs at the same time in the next cycle or, when that is not possible, to have the next cycle started with only one of the IMPs; and to allow treatment re-start with the re-administration of a loading dose of 9 mg/kg after 2 consecutive doses of S95026 have been omitted, in order to re-achieve steady state and target saturation after treatment interruption, in line with the rationale for the initial loading dose at C1D1. - Revised text in Section 9.1.1.3 to align with amended main ICF. - Added timepoint in Section 9.6 and investigation schedule. - Revised subgroup analyses and exploratory analyses in Section 10.1.2.4.2.1. - Added text regarding the PK and PK/PD analysis in Section 10.3.2. - Revised text regarding composition of SC members in Section 12.4.1. - Text regarding ICF availability in electronic format added in Section 13.3. - Added text regarding confirming the authenticity of the data in the e-CRF in Section 14.1. - Updated Appendix 5 with current version of the EQ-5D-5L scale. - Added footnote in Appendix 9 regarding use of H1 antagonists. - Removed Part A in Appendix 10 due to FDA feedback. - Revised and added footnotes in Appendix 12.

SYNOPSIS

Name of the sponsor: I.R.I.S.	
Name of Finished Product: Futuximab/modotuximab (also known as S95026 or Sym004)	
Name of Active Ingredient: futuximab and modotuximab	

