6.1.1.5. Volume of Infusion

- 9 mg/kg dose will be delivered in a total volume of 500 mL.
- 6 mg/kg dose (or lower in the event of a dose reduction) will be delivered in a total volume of 250 mL.

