8.11.2.3. Dose Reduction

In the event of Grade 3 treatment-related AEs, the participant may continue on study if there is evidence of clinical benefit as judged by the treating physician, but could do so at a reduced dose of futuximab/modotuximab once retreatment criteria are met ([Section 6.1.5](#)) (specific instructions for dose reduction linked to IRR, dermatologic AEs, and hypomagnesemia, are provided in Appendices 9, 10 and 11, respectively). All dose reductions of futuximab/modotuximab must be documented on the appropriate page of the participant's e-CRF.

If toxicity is to be managed by dose reduction, the futuximab/modotuximab dose will be decreased as shown in ([Table \(8.11.2.3\) 1](#)). Dose reduction may occur either during treatment cycles, or between cycles, as clinically indicated.

Table (8.11.2.3) 1 - Dose reduction of futuximab/modotuximab

Starting dose (Dose level 0)	Dose level -1	Dose level -2
Futuximab/modotuximab*	6 mg/kg	4.5 mg/kg

*Note: Dose Reductions for 9 mg/kg loading dose not applicable. The number of dose reductions allowed is limited to 2

Abbreviations (in alphabetical order): kg, kilogram; mg, milligram

A maximum of 2 dose reductions for futuximab/modotuximab-related toxicity are allowed (to a minimum dose of 3 mg/kg). Do not re-escalate dose after it has been reduced.

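### The futuximab/modotuximab restart rules in Protocol 8.11.2.2 are not limited to participants still at full dose, and the Appendix 10 first-occurrence row gives no reduction at 4.5 mg/kg

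*Protocol*

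**What the plan says.** **Restart after a delay.** Protocol 8.11.2.2 first states: "Dosing may be restarted at the same dose, as clinically indicated". It then sets out two cases under the words "For treatment restart with no dose reduction". After one omitted dose the restart is at 6 mg/kg. After two, "it is recommended that dosing re-start with the re-administration of a loading dose of 9 mg/kg followed by weekly maintenance doses of 6 mg/kg". A restart with a reduction is referred to 8.11.2.3. Three consecutive omissions lead to discontinuation.

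**Reduction.** Section 8.11.2.3 steps the dose from 6 to 4.5 mg/kg and then to a floor of 3 mg/kg, with at most two reductions. It adds "Do not re-escalate dose after it has been reduced". The note under its table reads "Dose Reductions for 9 mg/kg loading dose not applicable", and the note under the Appendix 10 table repeats this. The section gives no restart dose by number of omitted doses.

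**Related dosing text.** Section 6.1.1.1 keeps participants "at that same assigned dose throughout the duration of the treatment period unless dose reduction is required". Section 6.1.1.5 does allow for reduced participants: "6 mg/kg dose (or lower in the event of a dose reduction"). The Amendment 2 summary gives the reload's purpose: "in order to re-achieve steady state and target saturation after treatment interruption". Section 8.12.4 and Appendix 9 require that a participant who continues after a Grade 3 infusion reaction has later infusions at a lower dose and a slower rate.

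**Appendix 10, Section B.** When a Grade 3 skin event improves only to Grade 2, the first-occurrence row gives a single target of 4.5 mg/kg, whatever the current dose. The second- and third-occurrence rows depend on the current dose and step 4.5 down to 3.0 mg/kg. Only the third-occurrence row says to stop at 3.0 mg/kg.

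**The concern.** The phrase "For treatment restart with no dose reduction" can mean that no reduction has ever been made, or that no further reduction is made at this restart. On the second meaning, a participant held at 4.5 or 3.0 mg/kg who misses two doses and recovers is reloaded at 9 mg/kg. That person has already needed a reduction and is restarting after a further toxicity. Two careful sites could therefore give the same participant different doses.

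The situation is foreseeable. Appendix 10 keeps a participant at the current dose after recovery to Grade 1 or better, including at second and third occurrences when an earlier reduction is likely. It also schedules reassessment at one and, if needed, two weeks.

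The Appendix 10 gap works the other way: a participant whom the table means to step down could stay at the same dose.

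**Working it through.** No sample size, power or error rate is involved. The check sets the rules side by side and compares doses.

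**A. Restart of a participant already reduced, with no further reduction**

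| Current dose | 8.11.2.2 after 1 omission | 8.11.2.2 after 2 omissions, first infusion | 8.11.2.3, ban on re-escalation |
|---|---|---|---|
| 4.5 mg/kg | 6 mg/kg (6/4.5 = 1.33 times) | 9 mg/kg (9/4.5 = 2.0 times, +4.5 mg/kg) | 4.5 mg/kg |
| 3.0 mg/kg | 6 mg/kg (6/3.0 = 2.0 times) | 9 mg/kg (9/3.0 = 3.0 times, +6.0 mg/kg) | 3.0 mg/kg |

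*Maintenance dose.* The opening sentence of 8.11.2.2, 6.1.1.1 and 8.11.2.3 all point to the current level. The 6 mg/kg wording is loose, but the ban on re-escalation answers it.

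*Reload after two omissions.* The ban on re-escalation points against 9 mg/kg. The loading-dose notes in 8.11.2.3 and Appendix 10 can be read as keeping any reload at 9 mg/kg, and the stated purpose of restoring target saturation fits a full reload. None of these says that a reduced participant is meant to be reloaded.

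*After a Grade 3 infusion reaction.* Section 8.12.4 and Appendix 9 require a reduced dose, so a 9 mg/kg reload would contradict them directly.

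*Timing.* On the nominal schedule, the earliest reload of a reduced participant follows a reduced dose on C1D8 and omissions on C1D15 and C1D22. The restart is then C2D1, which is Day 29: 29 − 8 = 21 days after the last dose and after the 28-day DLT window.

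**B. Appendix 10, Grade 3 skin event improving to Grade 2**

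| Current dose | First-occurrence row | Second-occurrence row | Third-occurrence row |
|---|---|---|---|
| 6.0 mg/kg | 4.5 (1 − 4.5/6.0 = 25% lower) | 4.5 (25% lower) | 4.5 (25% lower) |
| 4.5 mg/kg | 4.5 (1 − 4.5/4.5 = 0%) | 3.0 (1 − 3.0/4.5 = 33% lower) | 3.0 (33% lower) |
| 3.0 mg/kg | 4.5 (+1.5 mg/kg) | no entry | discontinue |

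A participant can be at 4.5 mg/kg before any Grade 3 skin event. Routes include a Grade 3 infusion reaction (8.12.4, Appendix 9) and hypomagnesemia with QTc prolongation, where Appendix 11 allows restart at a reduced dose. The rise at 3.0 mg/kg is barred by 8.11.2.3, and the two-reduction limit largely fills the blank cell, so the 3.0 mg/kg entries are table clean-up.

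**The case against.** The strongest defence is that 8.11.2.2 has two branches and every figure in the first is a full-dose figure, so that branch naturally covers participants at full dose. A reduced participant falls under 8.11.2.3, whose ban on re-escalation has no exception. If that ban overrides the 6 mg/kg maintenance dose, it is hard to see why the 9 mg/kg infusion in the same sentence should survive. The loading-dose note may mean only that reductions step down from 6 mg/kg. The Grade 3 infusion-reaction case is already answered by 8.12.4 and Appendix 9. The reload is only a recommendation, left to clinical judgement. In Appendix 10, a reader who finds that the first-occurrence target is no reduction can fall back on the general step-down in 8.11.2.3. Sites also had a Registration and Prescription guide (4.1.3.5) and a Pharmacy Manual (6.2), neither of which is available here.

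Most of this stands, and it is why the point is minor. Two things remain. The loading-dose note, printed twice, keeps the full-dose reload arguable. And 8.11.2.3 names Appendix 10 as the source of specific instructions for skin events, so its first-occurrence cell is not clearly overridden by the general rule.

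**Conclusion.** The point holds as a minor inconsistency in the dosing rules. In (A), 8.11.2.3 should prevail. What remains arguable is one infusion, after exactly two omitted doses, at 2 or 3 times the current level. In (B), the literal instruction at 4.5 mg/kg is a 0% reduction where the later rows give 33%.

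Three stronger readings are tempting but not supported:

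- *A reload would escape the overdose definition.* Section 8.5 sets 9 mg/kg for the loading dose and 6 mg/kg for other administrations. If a reload is not authorised for a reduced participant, a 9 mg/kg infusion may well count as an overdose.
- *At most about 5 of 25 participants could be affected.* This applies the phase 2 rate of adverse events leading to dose reduction on the 9/6 regimen (20.2%, Section 2.2.2): 0.202 × 25 = 5.05. That rate is for monotherapy, and Section 2.6 anticipates added risks with the combination, so it bounds nothing. Nor do the documents say how many reduced participants would omit two doses or have a first Grade 3 skin event. The number is unknown and probably small. The 25 is also the planned number; SAP Section 1 reports that the study stopped during the lead-in.
- *Trial results are distorted.* There is no effect on power, alpha, endpoints or DLT counts. Cumulative dose and dose intensity in SAP 5.2.1.4 use the doses actually given.

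**What to change.** 1. In Protocol 8.11.2.2, limit the 6 mg/kg and the 9-then-6 mg/kg restarts to participants who have never been dose-reduced. State that a participant at 4.5 or 3.0 mg/kg restarts at the current level with no 9 mg/kg reload. This agrees with 8.11.2.3, 8.12.4 and Appendix 9.
2. In Appendix 10, Section B, change the first-occurrence action on improvement to Grade 2 to a reduction of one dose level, with discontinuation at 3.0 mg/kg. Add the 3.0 mg/kg discontinuation entry to the second-occurrence row.

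The cost is wording in one section and two table rows, with no extra participants, visits or procedures. With the Randomised part cancelled, the change matters for lead-in participants still on treatment and for any later protocol that reuses this text.
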